7.2.1. Selection and Timing of Doses

Assignment to 1 of the 4 LY3298176 doses, dulaglutide 1.5 mg, or placebo will occur at randomization. There are no restrictions on the time of day each weekly dose is given, but it is advisable to administer SC injections on the same day and same time each week. The actual date and time of all dose administrations will be recorded in the subject's CRF. If a dose of study drug, including dulaglutide or its placebo, is missed, the patient should take it as soon as possible unless it is within 72 hours of the next dose, in which case that dose should be skipped and the next dose taken at the appropriate time.

7.2.2. Specific Restrictions/Requirements

Prior to beginning the study, patients will complete informed consent and baseline tests.

Throughout the study, patients may undergo medical assessments and review of compliance with restrictions before continuing in the study.

Patients will report to the clinical research site for safety assessments and will remain in the clinic until all procedures for that visit are complete and the investigator has deemed it safe to release the patient from the clinic. There will be no inpatient stays. In addition, patients will report to the clinical research site for PK-specific visits (Visits 5, 7, 9, and 12).

Meals/Diet – Patients shall fast for at least 8 hours overnight prior to each outpatient visit where fasting samples are drawn or weight measurements taken.

Alcohol – Alcohol will not be permitted 8 hours prior to the dosing day, until the patient has been discharged from the clinical research site.

Exercise – Patients will be advised to maintain their regular levels of physical activity/exercise during the study. When certain study procedures are in progress at the site, patients may be required to remain recumbent or sitting.

Blood donation – Study participants should be instructed not to donate blood or blood products during the study or for 8 weeks following the study.

Contraception – Male patients or their female partners of child-bearing potential must use reliable contraception during intercourse throughout the treatment period and for 3 months after the last dose of study drug (as the risk of LY3298176 to the unborn fetus is unknown). Female patients of childbearing potential, if sexually active, should use two forms of effective contraception, where at least one form is highly effective for the duration of the trial and for 30 days thereafter. Please see Appendix 7 for further details regarding contraception.

7.3. Blinding

This is a double-blind study. Although the patient and the investigator will know which dose group (1 mg, 5 mg, 10 mg, or 15 mg LY3298176) the patient is assigned to, they will not know whether the patient is receiving LY3298176, dulaglutide 1.5 mg, or placebo.

To preserve the blinding of the study, a minimum number of Lilly personnel will see the randomization table and treatment assignments before the study is complete.

Emergency codes, generated by a computer drug-labeling system, will be available to the investigator. These codes, which reveal the patient's treatment group when opened, may be opened during the study ONLY if the patient's well-being requires knowledge of the patient's treatment assignment.

Emergency unblinding for AEs may be performed through the IWRS, which may supplement or take the place of emergency codes generated by a computer drug-labeling system. This option may be used ONLY if the patient's well-being requires knowledge of the patient's treatment assignment. All calls resulting in an unblinding event are recorded and reported by the IWRS.

If an investigator, site personnel performing assessments, or patient is unblinded, the patient must be discontinued from the study. In cases where there are ethical reasons to have the patient remain in the study, the investigator must obtain specific approval from a Lilly clinical research physician (CRP) for the patient to continue in the study.

In case of an emergency, the investigator has the sole responsibility for determining if unblinding of a patient's treatment assignment is warranted. Patient safety must always be the first consideration in making such a decision. If the investigator decides that unblinding is warranted, the investigator should make every effort to contact the Lilly CRP prior to unblinding a patient's treatment assignment unless this could delay emergency treatment of the patient. If a patient's treatment assignment is unblinded, Lilly must be notified immediately.

Upon completion of the study, all codes must be returned to Lilly or its designee.

7.4. Dosage Modification

Adjustment in study drug dose level will be allowed for patients assigned to the LY3298176 10-mg and 15-mg groups. If a patient in a LY3298176 treatment group of 10 mg or 15 mg does not tolerate the target titrated dose for 2 weeks once the assigned dose is reached, in other words if the patient is still vomiting or has moderate to severe nausea and the investigator does not believe that the patient will tolerate the dose with further exposure, then the investigator may drop the dose back to the next lower dose. Thus, if a patient has reached the target dose of 10 mg and has vomiting or moderate to severe nausea for 2 weeks, then the patient's dose level may be dropped back to 5 mg and the patient may remain on 5 mg for the duration of the study. Similarly, the 15-mg dose would be dropped to 10 mg. The actual dose received should be recorded on the CRF each week. Dosing of concomitant metformin is discussed in Section 7.7.

7.5. Preparation/Handling/Storage/Accountability

The study site must store the study drug in a locked and secure environment. The study drug must be refrigerated (not frozen) at 2°C to 8°C. Dry ice should not be used for cooling. Patients will be provided with double-blinded vials containing lyophilized LY3298176 or LY3298176 placebo and Sterile Water for Injection (along with syringes) and SDPs containing dulaglutide or dulaglutide placebo, at clinic visits according to the Study Schedule. The patients will also receive insulated bags with cooling gel packs for use in transporting the study drug from the site to the home. Study drug in each participating country will be labeled according to the country's regulatory requirements.

Commercial metformin may be made available during the treatment period to patients who entered the trial on this agent. Appropriate use and storage information will be available by referring to the package insert.

7.6. Treatment Compliance

During the study, patients will be asked to return their unused study drug materials and completed diaries to the site so that their compliance may be assessed.

Patients who are significantly noncompliant will be permanently discontinued from study medication. A patient will be considered significantly noncompliant if he/she intentionally misses 4 or more doses of study medication. Similarly, a patient will be considered significantly noncompliant if he/she is judged by the investigator to have intentionally or repeatedly taken more than the prescribed amount of medication.

7.7. Concomitant Therapy

Treatment with drugs that are excluded in the entry criteria (Section 6) is not permitted.

The only concomitant antihyperglycemic medication permitted during this study is metformin, unless glycemic criteria for rescue therapy are met (see Section 7.8.1). Metformin treatment must be stable for at least 3 months prior to screening at a daily dose of ≥1000 mg/day. Patients who enter the study on diet and exercise alone will not be allowed to initiate metformin therapy after study entry unless criteria for rescue therapy are met.

Patients who are being treated with metformin upon entering this study should remain on the same (or equivalent if switching to sustained release) metformin dose throughout the course of the study unless a change in dose is required to protect patient safety.

If a patient switches from the immediate-release formulation of metformin to the sustained-release formulation, the change will be on a milligram-per-milligram basis.

In certain situations (such as during a hospitalization or perioperatively), it may be necessary for a patient to be treated with insulin(s). Treatment with insulin will be allowed for up to 14 consecutive days prior to or during the trial. If a patient requires treatment with insulin for more than 14 consecutive days, that patient will be considered a "rescue" patient and may remain in the study but will not receive additional study drug.

Doses of antihypertensive and lipid-lowering therapies must be stable for 30 days prior to screening. Doses of antihypertensive and lipid-lowering agents should not be changed during this study unless necessary to protect patient safety on an emergency basis (e.g., hypertensive crisis).

Doses of other prescription medications (e.g., thyroxine, estrogen or progesterone replacement, or selective estrogen receptor modulators) for treatment of concurrent medical conditions should remain constant during the study whenever possible.

If the need for additional concomitant medication arises, the patient may be continued in the study on study medication if, in the investigator's opinion, the addition of the new medication does not pose a safety risk. If an additional concomitant medication is started, the sponsor should be informed as soon as possible. Nausea and/or vomiting during this study may be treated with antiemetics that do not increase QTc (e.g., cyclizine or meclizine) but should not be used prophylactically. Nonsteroidal anti-inflammatory medications (including ibuprofen, aspirin), acetaminophen, cough suppressants, antihistamines, vitamin/mineral supplements, antibiotics, and topical ointments may be used on an as-needed basis without notifying the sponsor and are not restricted by the stable dosing requirements listed above. Any additional

medication used during the course of the study (including those not requiring sponsor notifications) must be documented on the appropriate electronic case report form (eCRF).

Specifically_excluded concomitant medications include the following:

- Chronic use of drugs that directly reduce GI motility including but not limited to anticholinergics, antiemetics, and opiates (e.g., metoclopramide, phenergan, dicyclomine, and morphine)
- Chronic use of medications that directly promote motility (e.g., bethanechol and cisapride)
- Prescription or over-the-counter medications to promote weight loss
- Systemic glucocorticoid therapy of greater than 14 consecutive days' duration (with the exception of topical, intranasal, intraocular, intra-articular, and inhaled preparations)
- Central nervous system stimulants (e.g., Ritalin-SR)
- Any drug, other than those provided in this study, that has not received regulatory approval.

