- [27] Have an active or untreated malignancy or have been in remission from a clinically significant malignancy (other than basal or squamous cell skin cancer, in situ carcinomas of the cervix, or in situ prostate cancer) for less than 5 years prior to screening.
- [28] Have evidence of human immunodeficiency virus (HIV) and/or positive HIV antibodies historically or at screening.
- [29] Evidence of hepatitis B and/or positive hepatitis B surface antigen or evidence of hepatitis C.
- [30] Have a history of a transplanted organ (corneal transplants [keratoplasty] allowed).
- [31] Have evidence of a significant active, uncontrolled medical condition or a history of any medical problem capable of constituting a risk when taking the study medication or interfering with the interpretation of data, as judged by the screening investigator at screening.
- [32] Have had a significant change in weight, defined as a gain or loss of at least 4 kg (9 lb) in the 3 months prior to screening.

- [33] Have had a blood donation of 450 mL or more in the prior 3 months of screening or any blood donation within the prior month, or a blood transfusion or severe blood loss within the prior 3 months, or have known hemoglobinopathy, hemolytic anemia, sickle cell anemia, or have a hemoglobin value <11 g/dL (males) or <10 g/dL (females), or any other condition known to interfere with HbA1c methodology.
- [34] Have any other condition (including known drug or alcohol abuse or psychiatric disorder) that, in the opinion of the investigator, may preclude the patient from following and completing the protocol.

Prior/Concomitant Therapy

- [35] With the exception of stable doses of metformin, patients on another OAM (including, but not limited to, sulfonylureas, DPP-4i, sodium–glucose cotransport 2 inhibitors, alpha-glucosidase inhibitors, meglitinides) in addition to metformin therapy may be randomized if the additional OAM treatment was discontinued at least 3 months prior to screening.
- [36] Have used insulin for diabetic control within the prior year. However, short-term use of insulin for acute conditions is allowed (≤14 days) in certain situations, such as during a hospitalization or perioperatively (see Section 7.7).

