7.8. Treatment after the End of the Study

7.8.1. Special Treatment Considerations (Rescue Therapy)

Investigators will be trained on how to apply decision criteria for the timing and method of intervention in patients who do not reach glycemic targets during the 26-week treatment period. An additional therapeutic intervention should be considered in patients who meet the following criteria:

• The patients are fully compliant with assigned therapeutic regimen.

AND

- In the absence of any acute condition that raises blood glucose either of the following occurs:
 - Ouring the first 6 weeks post-randomization: An average fasting glucose level above 270 mg/dL (15.0 mmol/L) occurs over at least a 2-week period (at least 4 values/week must be available).

OR

O Any time after the first 6 weeks to 26 weeks post-randomization: An average fasting glucose level above 240 mg/dL (13.3 mmol/L) occurs over at least a 2-week period (at least 4 values/week must be available).

If these conditions are met, then patients may begin treatment with another antihyperglycemic agent as determined by their physician. If treatment with another antihyperglycemic agent is instituted, then study drug should be permanently discontinued. Patients may remain in the study for safety follow-up, but the date at which they begin rescue therapy will be the last date for collection of efficacy measures.

8. Discontinuation Criteria

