8.1. Discontinuation from Study Treatment

8.1.1. Permanent Discontinuation from Study Treatment

Discontinuation of the investigational product for abnormal liver tests **should be considered** by the investigator when a patient meets one of the following conditions after consultation with the Lilly-designated medical monitor:

- Abnormal liver tests or when a patient meets one of the following conditions:
 - o ALT or aspartate aminotransferase (AST) >8× ULN
 - o ALT or AST >5× ULN for more than 2 weeks
 - ALT or AST >3× ULN and total bilirubin level >2× ULN or prothrombin time >1.5× ULN
 - o ALT or AST >3× ULN with the appearance of fatigue, nausea, vomiting, right upper-quadrant pain or tenderness, fever, rash, and/or eosinophilia (>5%)
 - o Alkaline phosphatase (ALP) >3× ULN
 - \circ ALP >2.5× ULN and total bilirubin >2x ULN
 - o ALP >2.5× ULN with the appearance of fatigue, nausea, vomiting, right quadrant pain or tenderness, fever, rash, and/or eosinophilia (>5%)
- Investigator Decision
 - the investigator decides that the patient should be discontinued from the study medication
- Any medication for weight loss is given for more than 1 week
- Adverse Event
- When any one of the following events occur, Lilly or its designee is to be alerted immediately:
 - o Pancreatitis or pancreatic cancer (refer to Section 9.2.1.2.5 for details)
 - o Estimated glomerular filtration <30 mL/min
 - Any severe injection site reaction or 2 or more moderate injection site reactions occurring a week or more apart
 - o Any significant study drug-related hypersensitivity reaction
 - Any nonfatal major cardiovascular (CV) events (refer to Section 9.2.1.2.6 for details)
 - Any other treatment-emergent adverse event (TEAE), SAE, or clinically significant laboratory value for which the investigator believes that permanent study drug discontinuation is the appropriate measure to be taken.
- If the patient, for any reason (including protocol-mandated institution of rescue therapy; see Section 7.8.1), requires treatment for greater than 1 week with another therapeutic agent that has been demonstrated to be effective for treatment of diabetes. Also, a change in dose of metformin is not allowed (except for incidences of hypoglycemia; see Section 7.1). However, a change to an equivalent dose strength from immediate-release to extended-release (or vice versa) formulation is allowed.

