10.3. Statistical Analyses

10.3.1. General Statistical Considerations

Statistical analysis of this study will be the responsibility of Lilly or its designee. Any change to the statistical methods described in the protocol will require an amendment only if it changes a principal feature of the protocol. Any other change to the statistical analyses and the justification for the change will be described in the statistical analysis plan (SAP) and/or clinical study report. Additional exploratory analyses of the data may be performed as deemed appropriate. Analyses will be fully detailed in the SAP.

The intention-to-treat (ITT) population is defined as all randomized patients. Statistical analyses (including the primary analysis) will be conducted on the modified ITT (mITT) population. The mITT population is defined as all randomized patients with at least 1 post-baseline measurement according to the treatment the patients were assigned. The per-protocol (PP) population is defined as all randomized patients who were compliant with study drug and completed the protocol and is a subset of the mITT population. The safety population is defined as all randomized patients who have received at least 1 dose of study drug. Safety analyses will be performed on the safety population.

Some efficacy measures will also be analyzed on the PP dataset. The PP analysis will include patients who meet the following additional criteria:

- Have been appropriately randomized
- Have not discontinued from the study for any of the early discontinuation criteria
- Have not missed 4 or more doses during the treatment period
- Have not been rescued or taken a concomitant antihyperglycemic medication besides metformin for more than 7 cumulative days during the treatment period

Patients who have had rescue therapy will be included in the mITT population, but not the PP population. The efficacy measures will be censored at the time of rescue for analyses using mITT population.

No adjustments for multiplicity will be performed.

All tests of treatment effects will be conducted at a one-sided alpha level of 0.1 and/or one-sided 90% confidence interval, unless otherwise stated.

The baseline value used for the analyses will be the last scheduled baseline value obtained for each patient prior to randomization.

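### For an insulin course of 8 to 14 days, Protocol 7.7 keeps the patient on study drug while Protocol 8.1.1 lists a permanent stop, and the two must be reconciled

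*Protocol*

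**What the plan says.** **Insulin during the trial.** Protocol 7.7 begins from a general rule: "The only concomitant antihyperglycemic medication permitted during this study is metformin, unless glycemic criteria for rescue therapy are met". It then makes room for insulin in certain situations, with hospital stays and surgery as examples: "Treatment with insulin will be allowed for up to 14 consecutive days prior to or during the trial". A patient who needs insulin for longer is labelled a rescue patient, who "may remain in the study but will not receive additional study drug". Exclusion criterion 36 in Protocol 6.2 uses the same limit and points to 7.7: "short-term use of insulin for acute conditions is allowed (≤14 days) in certain situations".

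**Permanent discontinuation.** Protocol 8.1.1 includes a criterion for anyone who "requires treatment for greater than 1 week with another therapeutic agent that has been demonstrated to be effective for treatment of diabetes". It applies whatever the cause, and it expressly covers rescue begun under 7.8.1. It does not exempt insulin and does not mention 7.7.

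**Rescue therapy.** Protocol 7.8.1 sets glycemic conditions for rescue and then says: "If treatment with another antihyperglycemic agent is instituted, then study drug should be permanently discontinued". It makes the start of rescue the last date for efficacy data.

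**Data handling.** Protocol 8.1.2 leaves data after study drug stop out of the primary analyses, and Protocol 10.3.1 censors at rescue. SAP 6.9 drops only post-rescue data from the primary analysis. For other efficacy analyses, unless specified, it drops data after rescue or after study drug stop.

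**Per-protocol set.** Protocol 10.3.1 requires that the patient has not been rescued or "taken a concomitant antihyperglycemic medication besides metformin for more than 7 cumulative days during the treatment period". SAP 6.3 and item 11 of SAP Appendix 3 use the same limit. The last row of Appendix 3 makes it an important deviation, with per-protocol exclusion, to stay on study drug after meeting a permanent discontinuation criterion.

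**The concern.** Insulin is plainly an agent effective for diabetes, and the 8.1.1 criterion applies whatever the reason for its use. A patient given, say, 10 days of insulin around an operation is therefore allowed to continue study drug by one section and meets a permanent stop criterion in another. Neither section refers to the other.

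Two things depend on the answer: whether the patient goes on receiving randomized treatment, and whether later HbA1c and body weight values enter several of the planned analyses. Identical clinical events could be handled differently at different sites, and a site that follows 7.7 to the letter would still be recorded as having broken a discontinuation rule.

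**Working it through.** No power, sample size or alpha figure is involved, so there is no stated result to reproduce. The check is to apply each rule to the same patient.

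**Step 1. Where the rules part.** Take one uninterrupted insulin course of L days for an acute condition, with the 7.8.1 rescue criteria not met. The rules are: 7.7 stops study drug if L > 14; 8.1.1 lists a stop if L > 7 (1 week = 7 days); the per-protocol set excludes if cumulative days > 7.

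| L (days) | Stop under 7.7 | Stop under 8.1.1 | Excluded from per-protocol set |
|---|---|---|---|
| 1 | no | no | no |
| 7 | no | no | no |
| 8 | no | yes | yes |
| 14 | no | yes | yes |
| 15 | yes | yes | yes |

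The rules disagree from day 8 to day 14, a band of 14 − 8 + 1 = 7 days. Any 7 consecutive days contain one scheduled weekly dose, so a site will have to choose in practice.

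**Step 2. What follows from the choice, for a course of 8 to 14 days.**

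| Consequence | Site follows 7.7 | Site follows 8.1.1 |
|---|---|---|
| Study drug | continues | stops permanently |
| Last row of SAP Appendix 3 | deviation | no deviation |
| SAP *on treatment without rescue* analyses | later data stay, unless the insulin counts as rescue | later data leave |
| Primary analyses as worded in Protocol 8.1.2 | later data stay | later data leave |
| SAP primary set, *mITT without rescue* | changes only if the insulin counts as rescue | changes only if the insulin counts as rescue |
| Per-protocol set | excluded | excluded |

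The fourth and fifth rows also show the protocol and the SAP differing on whether stopping study drug, by itself, removes data from the primary analysis.

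**Step 3. Does 7.7 insulin count as rescue?** Protocol 7.7 implies that it does not up to 14 consecutive days, and says that it does beyond. SAP 6.7 separates antihyperglycemic use for any reason from rescue for severe, persistent hyperglycemia, but the SAP does not apply that distinction to insulin under 7.7. For a course that passes 14 days, no text says whether rescue dates from day 1 of insulin or from day 15, a difference of 15 − 1 = 14 days in the censoring date.

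**Step 4. Rescue therapy itself.** Protocol 7.8.1 ties the stop to the start of the other agent. Protocol 8.1.1 names rescue under 7.8.1 as included in its criterion, yet requires more than 1 week of treatment. For rescue lasting 7 days or less, the first stops study drug and the second does not. This is a separate mismatch from the one over short-term insulin.

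**Step 5. Size.** Planned completers per arm are 300 × 0.9 / 6 = 45, as the protocol states. One affected patient is 1/45 = 2.2% of that number. This is a share of patients, not an estimate of bias.

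**The case against.** *The specific rule governs the general one.* Section 7.7 deals with short-term insulin directly, so it could be read as an exception to 8.1.1. Nothing in the protocol says so. The 8.1.1 criterion is expressly independent of the reason for treatment, and item 11 of SAP Appendix 3 adopts a limit of 7 days, not 14.

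*Section 8.1.1 is only advisory.* Its opening line speaks of discontinuation to be considered, but that line concerns abnormal liver tests. The bullet on other agents is an incomplete sentence, so its force is open to some argument. It nevertheless stands under the heading for permanent discontinuation, and the last row of Appendix 3 treats such items as criteria that a patient can meet.

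*The effect on results is not shown to be material.* This stands. No frequency is given, the disputed band is 7 days of continuous insulin within a 26-week study, and SAP 6.9 also plans analyses of key measures such as HbA1c and body weight on all available mITT data.

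Four stronger readings are tempting, and the documents do not support them:

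- A reader might infer that 7.8.1 makes perioperative insulin an immediate stop. Its stop sentence follows conditions that require the absence of any acute condition raising blood glucose, so by its terms it does not reach the insulin that 7.7 has in mind.
- A reader might extend the conflict to other diabetes agents. The 14-day allowance covers insulin only.
- A reader might see the per-protocol limit as a further contradiction. An analysis set may be stricter than what is clinically allowed, and a patient with 8 to 14 days of insulin is excluded whichever section the site follows.
- A reader might infer that the SAP primary analysis is censored differently by site. Stopping study drug alone does not remove data from that set.

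**Conclusion.** The contradiction between Protocol 7.7 and 8.1.1 is real and confined to insulin courses of 8 to 14 days. For those patients it decides whether study drug continues, whether the last-row deviation in Appendix 3 is recorded, and whether later data remain in the SAP on-treatment analyses and in the primary analyses as Protocol 8.1.2 words them. For the SAP primary set, the open question is narrower: whether such insulin counts as rescue. The different triggers in 7.8.1 and 8.1.1 for rescue therapy are a second, smaller inconsistency.

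The conclusion assumes that insulin falls within the class of agents in 8.1.1 and that 1 week means 7 days. The number of patients cannot be derived from the documents and may be small, and no change in the primary conclusion is shown. The point should be corrected because the rule cannot be followed as written.

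**What to change.** Reconcile Protocol 7.7, 7.8.1 and 8.1.1 so that they give one consistent rule for when another antihyperglycemic agent, including short-term insulin, ends study drug, with cross-references between them. The same edit should settle how the metformin-only statement in 7.7 sits with its insulin allowance. Which limit applies is a clinical decision for the sponsor, and this review does not propose one.

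In the SAP, state whether insulin under 7.7 counts as rescue, give the date from which data are censored (including for a course that passes the limit), and align SAP 6.9 with Protocol 8.1.2 on data after study drug stop. Check the last row of Appendix 3 against the reconciled rule, so that a site following the protocol does not generate a deviation.

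The cost is protocol and SAP wording, with a note to sites. No change to sample size, visits or data collection is needed.
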